9 STATISTICAL METHODS

9.1 Determination of Sample Size

The sample size for this study is 400 subjects: 200 to be randomized to graded exercise, and 200 to be randomized to passive stretching. A power calculation was conducted with the minimum difference in probability of symptom recovery of 13%. Specifically, the probability of symptom resolution of passive stretching and graded exercise groups were set to be 80% and 93%, respectively. In order to achieve power of 90% with $\alpha=0.05$, a sample of 316 subjects is required. Allowing the attrition rate of 15%, a total of 363 subjects is required. To be conservative we plan to enroll 400 subjects to appropriately power this study.

9.2 Statistical and Analytical Plans

A Statistical Analysis Plan (SAP) will be written after finalizing the protocol and prior to database lock. The SAP will detail the implementation of all the planned statistical analysis in accordance with the principal features stated in the protocol. Any deviations from the SAP will be presented in the final clinical study report.

In general, data will be summarized using descriptive statistics (mean, median, standard deviation, minimum and maximum) or frequency counts and percentages, as appropriate to the type of data. Baseline will be defined as the last available, valid, non-missing assessment prior to dosing.

Only data from protocol scheduled visits/time points will be included in the summary tables. Data from unscheduled visits/time points will not be included in the summary tables but will be included in the figures and listings.

All analyses will be performed using Statistical Analysis Software 9.4 (SAS Institute, Cary, NC) and R 3.4.3 (R Foundation for Statistical Computing, Vienna, Austria; <http://www.r-project.org/>).

9.3 Analysis Populations

9.3.1 All Subjects Population

The all subject's population will include all enrolled subjects and will be based on the randomized intervention regardless of which intervention the subject actually completed. The all subject's population will be used for all summaries of baseline and demographic data.

9.3.2 Safety Population

The safety population will include all randomized subjects who completed at least Day 1 of therapeutic intervention and will be based on the actual therapy received, if this differs from that to which the subject was randomized to. The safety population will be used for the summaries of all safety data.

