4 STUDY DESIGN AND ENDPOINTS

4.1 Description of the Study Design

This study is designed as an open label study of a therapeutic intervention in subjects who have sustained mTBI. At least 400 subjects aged 14 to 45 inclusive will be enrolled in this study at up to 5 study sites. Subjects will be randomly assigned with a ratio of 1:1 to complete either graded exercise or passive stretching. The study sites will have well-established concussion research programs and referral populations.

The therapeutic intervention is either 20 minutes daily of graded exercise or 20 minutes daily of passive stretching delivered through the ClearPlay© mobile application, downloaded to an Apple i-touch or i-phone device, used in conjunction with a wrist-worn heart rate monitoring device (Waveband®). The sponsor will provide one i-touch or i-phone to each subject to provide them with access to ClearPlay App. This device will also allow subjects to access music for use during exercise or stretching.

Randomization of each subject will occur when the subject has completed all of their Baseline physiologic testing (Ice Bucket Test, ClearHeart© and BCBT) on Day 0.

[figure not shown]
Both the site staff treating subjects and the subjects themselves will be aware of the assigned exercise regimen. Subjects will be stratified based on baseline scores on the PCSS (threshold ≥ 30).

The study consists of 2 study visits and 3 remote telephone visits between the 2 study visits:

- Study Visit 1 (Day 0) – Screening/Baseline visit: within 3 to 14 days of concussion. This visit will serve as a screening visit, to determine eligibility to participate in the study. Eligible subjects will be enrolled, and baseline assessments performed;
- Remote telephone safety assessments – Day 14, Day 28 and Day 42 for safety follow up;
- Study Visit 2 – Follow-up visit: 8 weeks following enrolment (Day 56).

A schematic diagram of the study design is presented in Figure 2.

Figure 2: Study Design

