4.2 Study Objectives and Endpoints

The study objectives and endpoints to be evaluated in this study are presented in Table 1.

Table 1: Study Objectives and Endpoints

Objectives	Endpoints
Primary Objectives	Primary Endpoints
To compare the effects of graded exercise to passive stretching using ClearPlay© on symptomatic recovery rate following mTBI.	
 • Within-subject analysis of change in symptoms over time using the PCSS, comparing short-term ‘survival rates’ between graded exercise and stretching using Kaplan-Meier analyses for days since concussion.
Secondary Objectives	Secondary Endpoints
To compare the safety and tolerability of graded exercise to passive stretching in patients following mTBI.	
 • Adverse events reported from Day 1 through Day 56, including those identified during exercise or passive stretching during the 20 minutes of daily therapy.
To compare symptom resolution following graded exercise compared to passive stretching using ClearPlay© following mTBI.	
 • Within subject analysis of change in the number of subjects who are symptom free at 8 weeks between the 2 groups. Symptom free is defined by subjects having 3 consecutive days of PCSS scores lower than pre-concussion. 
Note: This objective is similar to the primary one, with the primary endpoint being recovery (binary outcome) vs. symptom resolution (continuous variable).
 
 • Determine differences in symptomatic recovery based on gender, baseline scores on the PCSS, baseline athletic fitness (Godin leisure-time exercise questionnaire), the history of injury, a history of migraine, as well as the presence of pre-morbid anxiety.
To compare the effects of graded exercise to passive stretching using ClearPlay© on physiologic recovery rate following mTBI.	
 • Within subject analysis of normalization of physiologic measurements obtained during the BCBT comparing data collected on entry to the study on Day 0 vs. follow up on Day 56 including: 
 - Beat to beat BP; • Determine differences in physiologic recovery based on gender, baseline scores on the PCSS, baseline athletic fitness (Godin leisure-time exercise questionnaire), the history of injury, a history of migraine, as well as the presence of pre-morbid anxiety (BAI; BSI-18; ASI).

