7.1.5.11 Recording of Adverse Events

Adverse events will be recorded and reported from Day 1 to Day 56. Adverse events will be captured at clinic visits on Day 1 and Day 56, and at telephone safety visits on Day 14, Day 28 and Day 42.

When an AE/SAE occurs, it is the responsibility of the investigator to review all documentation (eg, hospital progress notes, laboratory, and diagnostic reports) relative to the event. The investigator will then record all relevant information regarding an AE/SAE in to the eCRF. All details of any treatments initiated due to the AE should also be recorded in the subjects' notes and the eCRF.

Each AE will be documented in the subject's eCRF. If an AE changes in frequency or intensity during a study, a new entry of the event must be made in the eCRF.

In the event where the principal investigator is not a clinician, then the principal investigator must delegate the safety review duty to a clinician.

The investigator will attempt to establish a diagnosis of the event based on signs, symptoms, and/or other clinical information. In the absence of a diagnosis, the individual signs/symptoms should be documented.

All AEs occurring during the study must be documented on the relevant eCRF pages. The following data should be documented for each AE:

- Description of the symptom event;
- Classification of ‘serious’ or ‘not serious’;
- Severity;
- Date of first occurrence and date of resolution (if applicable);
- Action taken;
- Causal relationship;
- Outcome of event (unknown, recovered, not yet recovered, recovered with sequelae, death [with date and cause reported]).

After the initial AE or SAE report, the investigator is required to proactively follow each subject and provide further information to the sponsor on the subjects’ condition.

All AEs are required to be assessed by a medical practitioner. All AEs or SAEs documented at a previous visit/contact that are designated as ongoing, will be reviewed at subsequent visits/contacts. All AEs or SAEs will be followed until resolution, until the condition stabilizes, until the event is otherwise explained, or until the subject is lost to follow-up. The investigator will ensure that follow-up includes any supplemental investigations as may be indicated to elucidate the nature and/or causality of the AE or SAE.

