9.5 Safety Analysis

9.5.1 Adverse Event Analysis

Adverse events will be coded using the Medical Dictionary for Regulatory Activities (MedDRA). AEs will be grouped by system organ class and preferred term and summarized, by treatment group at the time of onset of the AE (ie, the therapeutic intervention most recently prior to the onset of the AE). The summary tables will present the number and percentage of total subjects and number of events, by system organ class and by preferred term.

All AE summaries will be restricted to treatment emergent AEs only. Treatment emergent AEs are defined as AEs which commence on or after the time of start of therapeutic intervention.

For the summaries of AEs, subjects who experience the same AE (in terms of the MedDRA preferred term) more than once will only be counted once for that event in the number of subjects but all occurrences of the same event will be counted in the number of events.

Separate summaries will be provided for AEs by severity and relationship to study intervention.

Serious adverse events will be summarized and listed separately.

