9.8 Handling of Missing Data

For subjects who are withdrawn from the study prior to their completion for any reason, all data compiled up to the point of discontinuation will be used for analysis. All withdrawals will be included in all analyses up to the time of withdrawal.

Subjects who are withdrawn prematurely from study intervention will be included in all analyses regardless of the duration of intervention.

There will be no imputation for missing data, unless otherwise stated.

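### The safety population requires completion of Day 1, which conflicts with the rules in 9.5.1, Table 1 and 9.8 and, read literally, drops first-session stops from the adverse-event tables

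*Protocol*

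**What the plan says.** Protocol section 9.3.2 sets the entry condition: "The safety population will include all randomized subjects who completed at least Day 1 of therapeutic intervention". Subjects are classified by the therapy actually received. The same section gives the set its purpose: "The safety population will be used for the summaries of all safety data". The protocol does not define what completing Day 1 means. Section 4.1 describes a day of therapy: "The therapeutic intervention is either 20 minutes daily of graded exercise or 20 minutes daily of passive stretching".

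Four other places bear on the same subjects:

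- Section 9.5.1, on which events are summarized: "Treatment emergent AEs are defined as AEs which commence on or after the time of start of therapeutic intervention".
- Section 7.1.5.11, on the recording window: "Adverse events will be recorded and reported from Day 1 to Day 56".
- Table 1 in section 4.2, on the safety and tolerability endpoint, which covers AEs from Day 1 onward, "including those identified during exercise or passive stretching during the 20 minutes of daily therapy".
- Section 9.8, on early withdrawal: "Subjects who are withdrawn prematurely from study intervention will be included in all analyses regardless of the duration of intervention".

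**The concern.** A safety set is normally defined by exposure, because exposure is what puts a subject at risk. Section 9.3.2 defines it by completing the first day, and intolerance of the first session is itself a reason for not completing it. Membership can therefore depend on the outcome that the set is meant to measure.

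The loss need not be equal between arms. Aerobic exercise soon after a concussion is more likely to be broken off for symptoms than passive stretching. Section 2.1 notes that exercise-induced headaches are among the most prevalent symptoms in the first week after injury, and enrolment can be as early as 3 days after it. Any imbalance of this kind would make the AE comparison look better for exercise.

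This is not a detail that can simply be left to the statistical analysis plan. The protocol fixes the population itself, and section 9.2 requires the SAP to follow the protocol's principal features. A SAP faithful to 9.3.2 would carry the condition forward.

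**Working it through.** The protocol states no figure on this point, so there is none to reproduce. The check is a reading of the rules against one case, followed by an illustration of size.

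**The rules applied to one case.** Take a subject who begins the first 20-minute session, stops because of an AE and does not resume.

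1. Section 7.1.5.11: the event falls on Day 1, so it is recorded.
2. Section 9.5.1: it began after therapy started, so it is treatment-emergent.
3. Table 1: it arose during the daily session, so it belongs to the safety endpoint.
4. Section 9.8: the subject left the intervention early and stays in all analyses.
5. Section 9.3.2: one day of therapy is one session, and that session was not completed. Read literally, the subject is outside the safety population and so outside the AE summaries.

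Steps 1 to 4 include the event or the subject, and step 5 excludes the subject. No text ranks 9.3.2 against 9.8. A programmer would probably apply 9.3.2, since it is the specific rule for safety tables.

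**Size.** The arm size comes from section 9.1: "200 to be randomized to graded exercise, and 200 to be randomized to passive stretching". Let k be the number of first-session AE stops in an arm who do not resume, and m the number of other subjects in that arm with an AE. Both are assumptions, since the protocol gives neither. Assume also that all 200 start therapy.

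- Incidence among all who started: (k + m)/200.
- Incidence under the completion rule: m/(200 − k).
- Difference: k(200 − k − m) / [200(200 − k)], which per excluded subject is 0.5 percentage points × [1 − m/(200 − k)].

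| k | m | All who started | Completed Day 1 only | Difference (points, before rounding) |
|---|---|---|---|---|
| 1 | 10 | 11/200 = 5.5% | 10/199 = 5.0% | 0.47 |
| 2 | 10 | 12/200 = 6.0% | 10/198 = 5.1% | 0.95 |
| 4 | 10 | 14/200 = 7.0% | 10/196 = 5.1% | 1.90 |
| 1 | 20 | 21/200 = 10.5% | 20/199 = 10.1% | 0.45 |
| 2 | 20 | 22/200 = 11.0% | 20/198 = 10.1% | 0.90 |
| 4 | 20 | 24/200 = 12.0% | 20/196 = 10.2% | 1.80 |

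Each excluded subject leaves both numerator and denominator. The reported incidence then barely moves with k, while the incidence among those who started rises by 0.5 points for each one.

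**The case against.** The strongest reply is that section 9.8 already covers this subject, so the protocol does not clearly exclude anyone. It also notes that completion is undefined and that section 9.3.1 uses the verb loosely, much as 9.3.2 speaks of therapy received. Completing Day 1 may simply have been meant as taking part on Day 1. This stands in part. It shows that exclusion is one reading and not a certainty. It does not remove the fault, because the two sections still disagree and the stricter wording sits in the definition of the safety set.

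Secondly, the data are not lost. AEs are recorded from Day 1, section 7.1.5.13 requires SAEs to be reported within 24 hours whatever their cause, and section 9.4 tabulates by randomized arm the size of each population and the reasons for early discontinuation. An imbalance in exclusions would be visible there. This stands. What is at risk is the set of AE summary tables by incidence, severity and relationship, and the SAE summary.

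A reader might go further in three ways that the documents do not support:

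- That the reported AE rate could be halved. With m = 10 this needs k = 10 (10.0% against 10/190 = 5.3%), so half of all subjects with an AE would have to abandon the first session for good. Nothing in the protocol suggests that frequency.
- That those affected are the subjects treated closest to injury. Every subject has a Day 1, at an interval set by enrolment 3 to 14 days after concussion.
- That Day 1 is the first exertion. All subjects do the bicycle test on Day 0, before randomization, and that test escalates until exhaustion or worsening symptoms. The daily exercise is then kept below the symptom threshold, and subjects unable or unwilling to exercise are excluded. These features make first-session stops less likely, and the number may be zero.

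**Conclusion.** The point holds as a conflict between rules, one of which selects on the outcome if applied as written. Section 9.3.2 must be reconciled with 9.5.1, Table 1 and 9.8. Under the literal reading, AE incidence in an arm of 200 is understated by roughly 0.5 percentage points per first-session AE stop who does not resume (0.45 to 0.47 in the illustrated cases).

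That figure assumes that all 200 subjects start therapy and that few other subjects have an AE. The number of such stops cannot be derived from the protocol. A heavier loss in the exercise arm is plausible but not quantified. A subject who breaks off on Day 1 and resumes later has no clear status either way.

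Severity is moderate. Safety and tolerability is a secondary objective, its analysis is descriptive with no planned test, and the primary analysis and sample size are untouched.

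**What to change.** In section 9.3.2, define the safety population as all randomized subjects who started any session of the therapeutic intervention, whether or not they completed it, analysed by therapy received. This agrees with the start-of-therapy window in 9.5.1, the endpoint in Table 1 and the withdrawal rule in 9.8. It also settles the status of subjects who break off and resume.

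The change should be made before database lock, so that in this open-label trial (section 6.3.1) membership is not decided with AE data in view.

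The cost is one phrase in the protocol and the matching line in the SAP, with no new data. The downside is that the reported AE rate may be slightly less favourable.

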9.3.3 Efficacy Population

The efficacy population will include all randomized subjects who completed, at least Day 1 of therapeutic intervention, who had PCSS data at baseline and at least 1 post-baseline assessment and will be based on the actual therapy received. The efficacy population will be

used for the summaries of all neuropsychology and autonomic data, and for the validation of ClearHeart© and ClearNeck© performance.

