7.4 Neuropsychology Testing

7.4.1 Post-Concussion Symptom Scale

The PCSS is a well validated 21-item self-report measure that records symptom severity using a 7-point Likert scale of severity. It ranks possible concussion symptoms by their severity to determine if a concussion has occurred, and whether further evaluation is required.

For all subjects, daily reported PCSS scores collected from ClearPlay© mobile application will be utilized to determine the resolution of symptoms.

This scale will be used to identify post-concussion symptom burden of each subject daily.

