9.6 Efficacy Analysis

The full presentation of the analysis of efficacy data will be presented in the SAP.

For all subjects, daily reported PCSS scores collected from ClearPlay© mobile application will be utilized to determine the resolution of symptoms. The resolution of symptoms is defined as a symptom-severity score of less than each subject's pre-injury PCSS score for 3 consecutive days. To assess differences in the probability of symptom resolution between graded exercise and passive stretching during the 8 weeks of therapy, both unadjusted and adjusted logistic regression models will be used. The primary outcome of the study will be to confirm or refute the superiority of sub-threshold aerobic exercise versus passive stretching to result in resolution of symptoms following mTBI. Confounders for the adjusted models will include age, gender, anxiety at baseline, history of migraine, cardiovascular fitness, the presence or absence of neurologic findings, and site of enrollment.

The survival probability will be compared using Kaplan-Meier (log rank test) analyses between the 2 treatment arms. Cox proportional hazards regression models will be used to evaluate the differences in time to symptom resolution. Adjusted treatment effects will be estimated in Cox proportional hazards regression models, controlling for the variables listed above. To identify that our randomization strategy was effective, analysis of variance will be used to assess for group-wise differences in age, days since injury to initial visit, initial PCSS score, resting HR, and Δ HR during the BCBT and resting BP and Δ BP during the ice bucket test on Day 1. Non-parametric tests of medians will be used to compare the non-normally distributed variable duration of clinical recovery. Chi-squared tests will be used to assess group-wise differences in gender, history of concussions, and incidence of PPCS.

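### The only efficacy set (9.3.3) groups subjects by therapy received and by conditions met after open allocation, and no as-randomised set is assigned to the superiority comparison

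*Protocol*

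**What the plan says.** Protocol section 9.3 defines three analysis sets.

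- **All Subjects (9.3.1).** The "population will include all enrolled subjects and will be based on the randomized intervention regardless of which intervention the subject actually completed". Its stated use is that this "population will be used for all summaries of baseline and demographic data".
- **Safety (9.3.2).** Randomised subjects who completed at least Day 1, grouped by therapy received.
- **Efficacy (9.3.3).** Randomised subjects who completed at least Day 1 of therapy, with baseline PCSS and "at least 1 post-baseline assessment and will be based on the actual therapy received". It is to be "used for the summaries of all neuropsychology and autonomic data", and for validating ClearHeart and ClearNeck.

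The primary endpoint in Table 1 (section 4.2) uses "Kaplan-Meier analyses for days since concussion". Section 9.6 defines resolution with the words "For all subjects, daily reported PCSS scores collected from" the mobile application. It plans unadjusted and adjusted logistic models and Cox models, and says: "The survival probability will be compared using Kaplan-Meier (log rank test) analyses between the 2 treatment arms". It names no analysis set for any of these.

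PCSS is described in 7.4.1, under the heading Neuropsychology Testing: "This scale will be used to identify post-concussion symptom burden of each subject daily".

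Subjects and staff know the allocation (6.3.1), which is made on Day 0 (6.3.2). Section 9.8 keeps subjects withdrawn early from the intervention in every analysis, however short their treatment. Section 4.3 gives the avoidance of subject-selection bias as the reason for randomising.

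**The concern.** A superiority comparison takes its validity from comparing the groups that randomisation formed. The one set that the protocol calls efficacy departs from those groups in two ways: it can move a subject to the other arm, and it keeps only subjects who met two conditions after learning their arm. (The third condition, baseline PCSS, comes before allocation and does no harm of this kind.)

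The outcome is self-reported. If subjects with a poor outlook skip the first session or never report more often in one arm, that arm's resolution rate rises with no treatment effect. This is the selection that section 4.3 says randomisation is there to avoid.

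The point is not that detail is missing. Section 9.2 says the SAP will follow the principal features of the protocol. Those features are an efficacy set grouped by therapy received and an as-randomised set reserved for baseline data. A SAP that follows them faithfully could carry 9.3.3 into the primary comparison.

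**Working it through.** **Step 1. Which set the text points to.**

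| Set | Grouping | Conditions after allocation | Stated use |
|---|---|---|---|
| 9.3.1 | randomised | none | baseline, demographics |
| 9.3.2 | received | Day 1 completed | safety |
| 9.3.3 | received | Day 1 completed; at least 1 post-baseline assessment | neuropsychology, autonomic, device validation |
| Comparisons in 9.6 | not stated | not stated | superiority on resolution |

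Two things link 9.3.3 to the last row: its name, and the placing of PCSS under 7.4. Two things weaken the link: 9.3.3 speaks of summaries, and the neuropsychology list in Table 4 (8.1) omits PCSS.

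**Step 2. The protocol's own sample size.** Section 9.1 gives 80% against 93%, alpha 0.05, power 90% and 316 subjects. The two-sided two-proportion formula with pooled null variance gives 143.1 per arm. With n = 143.1 and d = 0.13, the continuity correction n/4 × [1 + √(1 + 4/(n·d))]² gives 158.1 per arm. That is 316 in total, or 318 if each arm is rounded up. The figure is reproduced, so 80% and 93% are used below.

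**Step 3. Type I error if 9.3.3-type exclusion is applied.** From 9.1: 200 per arm and 80% resolution, here in both arms (no effect). Assumed, because the protocol gives no such figures: a share x of the exercise arm and f·x of the stretching arm is excluded, and excluded subjects would resolve at rate q = 0.5. With m = 200x and k = 200fx:

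- exercise: p1 = (160 − q·m)/(200 − m), with 200 − m subjects
- stretching: p2 = (160 − q·k)/(200 − k), with 200 − k subjects
- two-sided 0.05 z test, pooled null variance

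Example, x = 0.10 and f = 0.5: p1 = 150/180 = 0.8333 and p2 = 155/190 = 0.8158. The false difference is 0.0175 with standard error 0.0395, a shift of 0.44 standard errors, and the rejection rate is 7.3%.

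| Exclusion pattern | x = 2% | x = 5% | x = 10% |
|---|---|---|---|
| Equal in both arms (f = 1) | 5.0% | 5.0% | 5.0% |
| Half as many in stretching (f = 0.5) | 5.1% | 5.5% | 7.3% |
| Exercise only (f = 0) | 5.3% | 6.8% | 13.2% |

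The false difference for exercise-only exclusion is 0.6, 1.6 or 3.3 percentage points, against a planned 13.

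Range over q: for f = 0.5, q = 0.6 gives 5.0%, 5.2%, 6.0% and q = 0.4 gives 5.1%, 5.8%, 9.2%. For f = 0, q = 0.6 gives 5.1%, 5.8%, 8.5% and q = 0.4 gives 5.5%, 8.2%, 20.2%.

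**Step 4. Log-rank test.** A simulation of 40,000 trials used exponential times on a daily grid to Day 56, 80% resolved overall, and excluded subjects who miss Day 1 but do report PCSS. It gave 5.2%, 5.5%, 7.3% for f = 0.5; 5.2%, 6.6%, 13.2% for f = 0; and about 5% for f = 1. Keeping all randomised subjects gave 4.8% to 5.2% throughout.

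**Step 5. Power when analysed as randomised.** Suppose a share x of the exercise arm never starts and resolves at the stretching rate. The exercise rate becomes 0.93(1 − x) + 0.80x. The 170 per arm is 200 × 0.85, from the 15% attrition in 9.1. No continuity correction.

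| x | Exercise rate | Power, 200 per arm | Power, 170 per arm |
|---|---|---|---|
| 0% | 0.9300 | 97.0% | 94.3% |
| 2% | 0.9274 | 96.3% | 93.2% |
| 5% | 0.9235 | 95.0% | 91.3% |
| 10% | 0.9170 | 92.2% | 87.5% |

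**The case against.** The strongest reply is that the protocol never assigns 9.3.3 to the superiority test. The use stated in 9.3.3 closely matches 9.6.2, which summarises neuropsychology, cold pressor, whiplash and bicycle test results by time point. The comparisons in the body of 9.6 open with wording about all subjects, and that section defers the full presentation to the SAP. This stands in part. A reader might infer that the protocol prescribes an as-treated primary analysis; the text does not say so, and an as-randomised reading is open. But the opening words of 9.6 describe where the PCSS data come from, not who is analysed in which arm, and 9.8 does not state the arm either.

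Four further objections:

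- **Compliance rule.** A reader might infer that 9.3.3 contradicts 6.4.4, which withdraws subjects after 7 days without upload. It does not. One rule governs staying in the study and the other membership of an analysis set, and a subject can be in the study but outside a set. The Day 1 condition may also mean a first day of therapy, not calendar Day 1.
- **Regrouping.** Moving subjects to the therapy received is probably rare. The software loaded is specific to the arm (Table 4), and 5.3.1 withdraws over-exercisers without reassigning them. This stands; the weight lies on the two conditions met after allocation.
- **Size.** A reader might take 13.2% as the expected error. It needs 10% exclusion in one arm, none in the other, and a poor prognosis among those excluded; nothing in the protocol supports that asymmetry.
- **Reach of the fix.** Subjects with no post-baseline PCSS add nothing to the log-rank or Cox analyses in any set. This stands; there the gain is limited to those who miss the Day 1 condition but later report.

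**Conclusion.** The point holds in limited form. The protocol fixes an efficacy set unsuited to a superiority comparison, assigns its only as-randomised set to other uses, and leaves 9.3.3 as the probable default for the test in 9.6. It also contradicts itself on one group: subjects who start but do not complete Day 1 are kept by 9.8 once withdrawn from the intervention, and are dropped by 9.3.3.

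The actual bias cannot be stated, because no Day 1 completion rate is given. On the assumptions shown, it is nil if exclusion and prognosis are the same in both arms, negligible at 2% exclusion, and moderate (7.3%) at 10% with half as many excluded from stretching. Larger values need exclusion confined to one arm or a worse prognosis among those excluded. This merits correction before the analysis; it does not show that the trial's result would be wrong.

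**What to change.** State in 9.3 and 9.6 that the primary logistic, log-rank and Cox comparisons include all randomised subjects in the arm to which they were randomised, with no Day 1 completion condition. Define that set by randomisation instead of enrolment. Keep 9.3.3 as a supportive set and for the ClearHeart and ClearNeck validation. Reword 9.8 so that it agrees with the sets. Leave the handling of subjects with no post-baseline PCSS to the SAP.

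The cost is a few sentences and no new data. The statistical price is modest dilution. In the non-starter scenarios above, power stays over the planned 90% at 200 per arm, but falls to 87.5% at 170 per arm with 10% non-starters. It therefore cannot be promised that power stays above 90% in every case.
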